# 9 BIOMARKERS

Plasma/serum concentrations of each biomarker (those specifically listed in section 10.3 of the protocol) at each study visit will be summarised descriptively by treatment group for each cohort. Mean (SD), minimum, maximum and median (quartile) for changes from baseline (period-specific; see Section 5.2.2) to each post-baseline visit will be summarised for each analyte. Values below the limit of quantification will be set to 0.

# 10 PHARMACOKINETIC ANALYSES

To explore the PK exposure-response relationship of two doses of orvepitant in the participants a Pop PK approach by nonlinear mixed effects modeling will be used in exposure-response set. Relationships will be explored graphically, using linear or smoothing functions to evaluate relationships. Further model based-analyses will be conducted, including non-linear mixed effects modelling (NONMEM®) of orvepitant to evaluate covariates and subsequent impact on biomarkers and clinical endpoints. The details of these analyses will be described in a separate Pop PK Data Analysis Plan and the data will be reported separately from the safety and efficacy findings.

Plasma concentrations of orvepitant will be summarised descriptively at the end of washout and week 4 of each treatment period. The following summary statistics will be presented; number of non-missing observations, mean, SD, coefficient of variation (CV%), median, minimum, maximum, geometric mean, CV% for geometric mean, and number of subjects below the lower limit of quantification (LLoQ). LLoQ will be substituted for below lower limit of quantification (BLLQ) values.

Separate summaries of orvepitant plasma concentrations will also be presented for the sub-groups taking pirfenidone and nintedanib concomitantly.

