10.3 Biomarkers

Serum/plasma will be collected for assessment of biomarkers at Visits 2, 4, 5 and 7.

Biomarkers to be assessed are:

Potential mechanistic / pharmacodynamic markers	• Monocyte chemo-attractant protein–1 (MCP-1)
	 Interleukin (IL)-1β
	• IL-6
	• IL-17A

Protocol No.: ORV-PF-01 Final V4.0 (US) Page 50 of 85

DRVEPITANT	NeRRe Therapeutics Ltd
Potential markers of	

Protocol No.: ORV-PF-01

Potential markers of disease progression	• C3M	
--	-------	--

10.4 **Pharmacokinetic Assessments**

A single 'spot' blood sample for analysis of plasma or vepitant concentrations will be collected at Visits 4, 5 and 7.

Details of PK blood sample collection (including volume to be collected), processing, storage and shipping procedures will be provided in the Laboratory Manual.

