11.10 Pharmacokinetics Analysis

The plasma orvepitant concentrations will used to confirm individual subject exposure to orvepitant and to explore exposure differences in the two doses being evaluated. The data may also be analysed using a population pharmacokinetic (Pop PK) approach by nonlinear mixed effects modeling (NONMEM®). The Pop PK model will be used to evaluate the relationship between orvepitant exposure and clinical endpoints. The details of the analysis will be described in a Pop PK Data Analysis Plan and the data will be reported separately from the safety and efficacy findings.

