### 2.6.4 Carry Over Effects

A potential limitation of any cross-over study is the occurrence of confounding carry over effects between treatment periods. The wash-out period for this study is 3-weeks which, given that the half-life of orvepitant is approximately 33 hours, is expected to be sufficient for the drug to be fully cleared and for cough symptoms to return to baseline levels.

Period-specific baseline values will be used in the analysis of primary and secondary efficacy endpoints, and safety endpoints, when available, to protect against possible carryover effect. Please refer to Section 5.2.2 for more details.

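### SAP 10 sets every orvepitant value below quantification to the LLoQ, so averages for placebo-period and end-of-wash-out samples cannot fall below the LLoQ even when no drug is present

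*SAP*

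**What the plan says.** Protocol 10.4 takes single spot samples: "concentrations will be collected at Visits 4, 5 and 7". Visit 5 is the only one between the last Period A dose and the first Period B dose. Protocol 11.10 gives the use of the data as "to confirm individual subject exposure to orvepitant" and exploring the difference in exposure between the two doses.

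SAP 10 states: "Plasma concentrations of orvepitant will be summarised descriptively at the end of washout and week 4 of each treatment period". Each subject takes placebo in one period, so this covers placebo-period samples. The statistics listed are the arithmetic mean, SD, CV%, median, minimum, maximum, geometric mean, geometric CV and a count of subjects below the LLoQ. The next sentence is the rule: "LLoQ will be substituted for below lower limit of quantification (BLLQ) values". It is not limited by visit, treatment or sequence, and no reason is given.

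Two other parts of the SAP bear on this. SAP 9, on biomarkers, says "Values below the limit of quantification will be set to 0". SAP 5.1 already has a method for geometric means of data containing zeros: add 1 to every value and subtract it afterwards. On wash-out, SAP 2.6.4 says that three weeks, with a half-life of about 33 hours, "is expected to be sufficient for the drug to be fully cleared".

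**The concern.** Substituting the LLoQ assigns a blank sample the ceiling of its possible range. That matters little when a few low values sit among many well-quantified ones. Here whole cells of the table should consist of blanks: Week 4 of the placebo periods, and Visit 5. Placebo-first subjects have had no drug at either Visit 4 or Visit 5. In those cells the rule, and not the data, sets the reported location statistics.

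What is at stake is the accuracy of a descriptive table. It has practical value because the crossover relies on clearance. Protocol 5.6 also reports that in the open-label pilot the fall in cough frequency appeared to last a further 4 weeks after treatment ended. If cough scores at Visit 5 had not returned to baseline, a reader would want to know whether drug was still present. A mean of at least 1 LLoQ in every group, including subjects never dosed, is a poor answer to that question.

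**Working it through.** The plan gives no figure to reproduce on this point. The check uses these inputs.

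| Input | Value | Source |
|---|---|---|
| Rule for values below the LLoQ | replaced by the LLoQ, no exception | SAP 10 |
| Samples | Visits 4, 5 and 7 | Protocol 10.4 |
| Half-life | about 33 h | SAP 2.6.4 |
| Wash-out | 21 days, ± 3 | Protocol 8.7.5 |
| Subjects, for scale only | 37 | SAP 2.5.1 |
| Assay LLoQ | not given; taken as 1 unit, or as an assumed 0.01% to 5% of the last-dose level | assumption |

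**The floor.** If every value entering the summary is at least L, then the mean, median, minimum and geometric mean are all at least L. This is exact and needs no assumption about the assay.

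**All 37 samples blank (L = 1).**
- LLoQ substituted: mean = median = minimum = geometric mean = 1.0, SD 0.
- LLoQ/2 substituted: 0.5 for each, SD 0.
- 0 substituted: 0 for each (geometric mean by the add-1 method of SAP 5.1), SD 0.
- Count below the LLoQ: 37 of 37 under every rule.

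**Three of 37 at 2 × LLoQ (assumed), 34 blank.**
- LLoQ: (34 × 1 + 3 × 2)/37 = 40/37 = 1.08.
- LLoQ/2: (34 × 0.5 + 3 × 2)/37 = 23/37 = 0.62.
- 0: (3 × 2)/37 = 6/37 = 0.16.
- Count below the LLoQ: 34 of 37 under every rule.

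Under the SAP rule the three real values move the mean only from 1.00 to 1.08.

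**Expected residue at Visit 5**, as a fraction of the last-dose level, is 0.5^(hours/33):
- 18 days: 432/33 = 13.1 half-lives, 0.011%.
- 21 days: 504/33 = 15.3 half-lives, 0.0025%.
- 24 days: 576/33 = 17.5 half-lives, 0.0006%.

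As an outer bound, the SAP 5.3.2 windows for efficacy data still accept Visit 4 at Day 34 and Visit 5 at Day 42. That gap is 8 days: 192/33 = 5.8 half-lives, about 1.8%.

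**Reported value against expected residue.** The ratio is the assumed LLoQ divided by the residue.

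| LLoQ as % of last-dose level (assumed) | 21 days | 18 days |
|---|---|---|
| 0.01% | 4.0 | 0.87 |
| 0.1% | 40 | 8.7 |
| 1% | 396 | 87 |
| 5% | 1,979 | 436 |

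Over most of this range, a Visit 5 mean of 1 LLoQ would come from the substitution and not from drug. At 0.01% and 18 days the residue would be just quantifiable.

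**Share of samples.** Take one subject per sequence with complete data: 6 samples. Two are from the placebo-first subject before any drug (Visits 4 and 5). One is the orvepitant-first subject's Visit 7, about 21 + 28 = 49 days after the last dose (1,176/33 = 35.6 half-lives). These three should be blank. A fourth, the orvepitant-first Visit 5, is blank or not depending on the LLoQ. The rule therefore sets between 3/6 and 4/6 of the values, before counting any subject who stopped orvepitant early.

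**The case against.** The strongest reply is that the table already discloses the censoring. SAP 10 requires the number below the LLoQ alongside the other statistics. A cleared group would show all subjects below the LLoQ, with minimum, median and maximum all equal to the LLoQ. A real residue would lower that count and, if above the LLoQ, would appear as the maximum; neither depends on the substitution. Protocol 11.6 and SAP 5.1 also provide listings of individual data. This stands. A reader might infer that the Visit 5 table would show apparent residual drug, or that wash-out could not be confirmed. The documents do not support that.

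Further points also stand:
- Neither document names Visit 5 as a test of wash-out. That use is an inference from its timing.
- A reader might infer that placebo-first subjects are pooled with orvepitant-first subjects at Visit 5 and dilute any signal. No text says so. The columns in SAP 12.2.5.2 could keep the sequences apart; how Visit 5 is assigned to those columns is not stated.
- An SD of 0 is not peculiar to this rule. All-zero data also give SD 0, and CV% is then undefined.
- SAP 9 is a different convention for a different kind of measurement, not a contradiction. It lists no geometric mean, whereas SAP 10 does. Zeros in SAP 10 would bring in the add-1 method, whose result depends on the units.

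None of this makes the reported mean, median, minimum or geometric mean right for a group with no drug. The objection to zeros in geometric means is met by not reporting geometric means where blanks dominate.

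**Conclusion.** The point holds as a defect in descriptive reporting. For placebo-period and Visit 5 samples, SAP 10 fixes a floor of 1 LLoQ under four location statistics whether or not drug is present, and it blunts the mean when a few values are quantifiable (1.08 against 0.16 LLoQ in the assumed example). The floor follows from the rule alone. The share of samples affected and the gap between the reported value and true residue depend on the assay LLoQ, which the documents do not give, and on first-order decline at 33 hours.

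The harm stops there. No efficacy test, sample size or error rate uses these summaries, and exposure-response modelling is left to a separate plan (SAP 10, Protocol 11.10). The change is worth making before unblinding because the rule is explicit, unexplained and easily corrected.

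**What to change.** Amend SAP 10 as follows.

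- Set values below the LLoQ to 0 in arithmetic summaries of placebo-period and Visit 5 samples.
- Report the geometric mean and geometric CV only for orvepitant Week 4 samples, where the present LLoQ substitution can remain.
- Where half or more of the values in a cell are below the LLoQ, show the count below the LLoQ, the median and the maximum in place of the mean and CV%.
- State that Visit 5 is shown by Period A treatment (that is, by sequence) within cohort, so that clearance is read from subjects who had received orvepitant.

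The cost is a few sentences in the SAP and one table shell, with no new data. The small drawback is that handling then differs between orvepitant Week 4 and the other samples; a table footnote can say so.

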## 11 INTERIM ANALYSIS

There is no formal interim analysis planned at this time. The final database lock will take place when the last subject has completed the last visit for the study.

Page 39 of 50

NeRRe Therapeutics Ltd Protocol: ORV-PF-01

# 11.1 DATA SAFETY MONITORING BOARD (DSMB)

A DSMB will be convened with the primary remit of providing independent safety oversight of the study.

The composition of the DSMB, its terms of reference and its operating procedures are described in the DSMB Charter which will be finalised before the first subject is randomised into the study. The DSMB membership will include an unblinded statistician who will be responsible for providing the DSMB with the agreed information necessary for the DSMB to undertake its assessments of safety.

## 12 SOFTWARE AND PROGRAMMING SPECIFICATIONS

All datasets, TLFs, and statistical analyses will be generated using SAS, Release 9.4 or higher (SAS Institute Inc., Cary, NC, USA). Computer-generated datasets, table, listing and figure output will adhere to the following specifications:

# 12.1 GENERAL PROGRAMMING SPECIFICATIONS

- One SAS program can create several outputs, or a separate SAS program can be created for each output at the statistical programmer's discretion.
- Each output will be stored in a separate file.
- Output files will be delivered in Word format / rtf format.
- Numbering of TLFs will follow ICH E3 guidance

# 12.2 TABLE, LISTING, AND FIGURE FORMAT

## **12.2.1** General

- All TLFs will be produced in landscape format, unless otherwise specified.
- All TLFs will be produced using the Courier New font, size 8.
- The data displays for all TLFs will have a 1.5-inch binding margin on top of a landscape-orientated page and a minimum 1-inch margin on the other 3 sides.
- Headers and footers for figures will be in Courier New font, size 8.
- Legends will be used for all figures with more than 1 variable, group, or item displayed.
- TLFs will be in black and white (no color), unless otherwise specified.
- Specialized text styles, such as bolding, italics, borders, shading, and superscripted and subscripted text, will not be used in the TLFs, unless otherwise specified. On some occasions, superscripts 1, 2, or 3 may be used (e.g., cm^2, Cmax).
- Only standard keyboard characters will be used in the TLFs. Special characters, such as non-printable control characters, printer-specific, or font-specific characters, will not be used. Hexadecimal-derived characters will be used, where possible, if they are appropriate to help display math symbols (e.g., μ). Certain subscripts and superscripts (e.g., cm², Cmax) will be employed on a case-by-case basis.
- Mixed case will be used for all titles, footnotes, column headers, and programmer-supplied formats, as appropriate.

Page 40 of 50

NeRRe Therapeutics Ltd Protocol: ORV-PF-01

## 12.2.2 Headers

• All output should have the following header at the top left of each page:

NeRRe Therapeutics Ltd Protocol: ORV-PF-01

- All outputs should have Page n of N at the top or bottom right corner of each page. TLFs should be internally paginated in relation to the total length (i.e., the page number should appear sequentially as page n of N, where N is the total number of pages in the table).
- The date (date output was generated) should appear along with program name and location as the last footer on each page.

# 12.2.3 Display Titles

Each TLF should be identified by the designation and a numeral. (e.g., Table 14.1.1). ICH E3 recommended numbering will be used. A decimal system (x.y and x.y.z) should be used to identify TLFs with related contents. The title is centered. The analysis set should be identified on the line immediately following the title. The title and table designation are single spaced. A solid line spanning the margins will separate the display titles from the column headers. There will be 1 blank line between the last title and the solid line.

Table x.y.z
First Line of Title
Second Line of Title (if needed)
Analysis Set

## 12.2.4 Column Headers

- Column headings should be displayed immediately below the solid line described above in initial upper-case characters.
- For numeric variables, include "unit" in column or row heading when appropriate.
- Analysis set sizes will be presented for each treatment group in the column heading as (N=xx) (or in the row headings if applicable). This is distinct from the 'n' used for the descriptive statistics representing the number of subjects in the analysis set.

# 12.2.5 Body of the Data Display

#### 12.2.5.1 General Conventions

Data in columns of a table or listing should be formatted as follows:

- alphanumeric values are left-justified;
- whole numbers (e.g., counts) are right-justified; and
- numbers containing fractional portions are decimal aligned.

Page 41 of 50

NeRRe Therapeutics Ltd Protocol: ORV-PF-01

## 12.2.5.2 Table Conventions

- Units will be included where available
- Data will be presented in the following order (left to right or top to bottom, as appropriate) in tables: placebo (Cohort 2), orvepitant 10 mg, placebo (Cohort 1), orvepitant 30 mg.
- If the categories of a parameter are ordered, then all categories between the maximum and minimum category should be presented in the table, even if n=0 for all treatment groups in a given category that is between the minimum and maximum level for that parameter. For example, the frequency distribution for symptom severity would appear as:

Severity Rating	N
very severe	2
severe	0
moderate	8
mild	3

Where percentages are presented in these tables, zero percentages will not be presented and so any counts of 0 will be presented as 0 and not as 0 (0%).

- If the categories are not ordered (e.g., Medical History, Reasons for Discontinuation from the Study, etc.), then only those categories for which there is at least 1 subject represented in 1 or more groups should be included.
- An Unknown or Missing category should be added to any parameter for which information is not available for 1 or more subjects.
- Unless otherwise specified, the estimated mean and median for a set of values should be presented to 1 more significant digit than the original values, and standard deviations should be presented to 2 more significant digits than the original values. The minimum and maximum should report the same significant digits as the original values. For example, for systolic blood pressure:

N	XX
Mean	XXX.X
Std Dev	X.XX
Median	XXX.X
Minimum	XXX
Maximum	XXX

- P-values should be output in the format: "0.xxx", where xxx is the value rounded to 3 decimal places. Any p-value less than 0.001 will be presented as <0.001. If the p-value should be less than 0.0001 then present as <0.0001. If the p-value is returned as >0.999 then present as >0.999
- Percentage values should be printed to one decimal place, in parentheses with no spaces, one space after the count (e.g., 7 (12.8%), 13 (5.4%)). Values that round down to 0.0 will be displayed as '<0.1'. Unless otherwise noted, for all percentages, the number of subjects in the analysis set for the treatment group who have an observation will be the denominator. Percentages after zero counts should not be displayed and percentages equating to 100% should be presented as 100%.

Page 42 of 50

NeRRe Therapeutics Ltd Protocol: ORV-PF-01

- Unless otherwise specified, tabular display of data for medical history, prior / concomitant medications, and all tabular displays of adverse event data should be presented by the body system, drug class, or SOC in descending order, assuming all terms are coded. Within the body system, drug class and SOC, medical history (by preferred term), drugs (by ATC code), and adverse events (by preferred term) should be displayed in decreasing order. If incidence for more than 1 term is identical, they should then be sorted alphabetically. Missing descriptive statistics or p-values which cannot be estimated should be reported as "-".
- The percentage of subjects is normally calculated as a proportion of the number of subjects assessed in the relevant treatment group (or overall) for the analysis set presented. However, careful consideration is required in many instances due to the complicated nature of selecting the denominator, usually the appropriate number of subjects exposed. Details of this will be provided in footnotes in tables where appropriate.
- For categorical summaries (number and percentage of subjects) where a subject can be included in more than one category, a footnote will note if the subject should be included in the summary statistics for all relevant categories or just 1 category and the criteria for selecting the criteria.
- Where a category with a subheading (such as system organ class) has to be split over more than one page, output the subheading followed by "(cont)" at the top of each subsequent page. The overall summary statistics for the subheading will only be output on the first relevant page.

# 12.2.5.3 Listing Conventions

- Listings will be sorted for presentation in order of treatment groups (as above), subject number, visit/collection day, and visit/collection time.
- Missing data will be represented on subject listings as either a hyphen ("-") with a corresponding footnote ("- = unknown or not evaluated"), or as "N/A", with the footnote "N/A = not applicable", whichever is appropriate.
- Dates will be printed in SAS® DATE9.format ("DDMMMYYYY": 01JUL2000). Missing portions of dates will be represented on subject listings as dashes (--JUL2000). Dates that are missing because they are not applicable for the subject are output as "N/A", unless otherwise specified.
- All observed time values will be presented using a 24-hour clock HH:MM or HH:MM:SS format (e.g., 11:26:45, or 11:26). Time will only be reported if it was measured as part of the study.
- Units will be included where available

# 12.2.5.4 Figure Conventions

• Unless otherwise specified, for all figures, study visits will be displayed on the X-axis and endpoint (e.g., treatment mean change from baseline) values will be displayed on the Y-axis.

## 12.2.6 Footnotes

• A solid line spanning the margins will separate the body of the data display from the footnotes.

Page 43 of 50

NeRRe Therapeutics Ltd Protocol: ORV-PF-01

- All footnotes will be left justified with single-line spacing immediately below the solid line underneath the data display.
- Footnotes will always begin with "Note:" if an informational footnote, or 1, 2, 3, etc. if a reference footnote. Each new footnote will start on a new line where possible.
- Footnotes will be present on the page where they are first referenced and thereafter on each page of the table, unless the footnote is specific only to certain pages. Subject specific footnotes will be avoided wherever possible.
- Footnotes will be used sparingly and must add value to the table, figure, or data listing. If more than six lines of footnotes are planned, then a cover page may be used to display footnotes, and only those essential to comprehension of the data will be repeated on each page.
- The last 2 lines of the footnote section will be a standard source that indicates the name of the program used to produce the data display, date the program was run, and the listing source (or data source for a listing) (e.g., 'Program: myprogram.sas Listing source: 16.x.y.z').

Page 44 of 50

# 13 QUALITY CONTROL

## 13.1 SPECIFICATIONS

Once the SAP is finalised, dataset and TLF specifications will be developed and reviewed by the study team. A round table review of draft specifications will be conducted by the Programmer, Lead Validator, Lead Statistician and Senior Reviewer (or member of Statistics Management).

NeRRe will then review, comment and approve (via signature) this analysis plan and all dataset and TLF specifications as well as any subsequent amendments to any of these.

